For Grade 1-2 infusion reactions, daratumumab can be resumed at half the rate at which the reaction occurred. Further escalation of the rate is still possible providing the patient does not experience any further reactions.

For Grade 3 reactions, the infusion can be restarted at half the rate once the intensity of the reaction has decreased to a Grade 2 level or lower. Further escalation of the rate is still possible providing the patient does not experience any further reactions. The above instructions can be repeated if another Grade 3 reaction occurs. Permanent discontinuation of daratumumab should be undertaken if a third Grade 3 or greater reaction occurs.

For Grade 4 reactions (life threatening), daratumumab should be discontinued permanently.

Non-reaction Daratumumab-Related Toxicity Management

The criteria for a dose delay are:

- Grade 4 hematologic toxicities
- Grade 3 thrombocytopenia with bleeding
- Febrile neutropenia of any grade
- Neutropenia with infection, of any grade
- Grade 3 or higher non-hematologic toxicities with the following exceptions:
 - Grade 3 nausea that responds to antiemetic treatment within 7 days
 - Grade 3 vomiting that responds to antiemetic treatment within 7 days
 - Grade 3 diarrhea that responds to antidiarrheal treatment within 7 days
 - Grade 3 fatigue that was present at baseline or that lasts for <7 days after the last administration of daratumumab
 - Grade 3 asthenia that was present at baseline or that lasts for <7 days after the last administration of daratumumab

Daratumumab Delays

Administration of daratumumab may be restarted upon recovery from toxicity to Grade 2 or baseline, with the exception that Grade 2 laryngeal edema or Grade 2 bronchospasm must be fully recovered. If more than 2 consecutive planned doses of daratumumab are missed due to adverse events, treatment should be permanently discontinued. If 2 consecutive doses of daratumumab are missed for any reason other than adverse events, this should be brought to the attention of the Sponsor at the earliest possible time and study treatment should be discontinued, unless, upon consultation with the sponsor and the review of data, continuation is agreed upon.

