11.2 Interim Analysis

The study will be temporary closed for an interim analysis after the first 5 patients have completed at least 3 doses. At this time the Medical Monitor will review the safety results of the study. The recommendation is to consider stopping the study for safety concerns if during this time (3 doses for the first 5 patients) 3 or more grade 4 or 5 adverse events clearly related to study drug are recorded. If 3 or more out of the first 5 patients experience a Grade 3 infusion reaction clearly related to study drug in either of the first 3 doses, the protocol will be re-evaluated to consider modifying the schedule of daratumumab (for example, split the first dose of daratumumab over two days or adding mandatory concomitant medications). If fewer than 3 out of the first 5 patients experience a Grade 3 infusion reaction in either of the first 3 doses, the study will re-open and enrollment will be expanded to an additional cohort of subjects.

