12.0 DATA AND SAFETY MONITORING PLAN

Toxicity and accrual monitoring will be performed on a routine basis by the study investigators as well as the multidisciplinary members of the Amyloid Center at Boston University, which has over 40 years' experience in the treatment of AL amyloidosis. Subjects will undergo toxicity assessment, performance status assessment and laboratory tests before each dose. Response assessment will be conducted every three months. The clinical status and laboratory reports of the study participants will be reviewed routinely by treating physicians. Dose modifications/interruptions or discontinuation will be implemented according to Section 8.

In addition, a Medical Monitor will be assigned to the study. The Medical Monitor must be a qualified clinician with relevant expertise, but no direct connection with the research, whose primary responsibility is to provide independent safety monitoring in a timely fashion. The PI will submit a

report to the Medical Monitor, at a minimum of once every 6 months, including a list of all adverse events and serious adverse events (regardless of relatedness). In addition, any unanticipated problems involving risks to participants or others and participant deaths within 30 days of study intervention will be reported to the Medical Monitor within 48 hours. The Medical Monitor is expected to provide a formal, unbiased written report evaluating individual and cumulative participant safety data when making recommendations regarding continuation of the study. Although the PI is responsible for assigning causality, the medical monitor will comment on whether or not (s)he is in agreement. Medical Monitor reports will must be submitted to the PI following each review (at a minimum of once every 6 months), which the PI will, in turn, submit to the IRB. Although there is no pre-determined criteria for early termination due to toxicity, the Medical Monitor and investigators will evaluate toxicities on a continuing basis, and will terminate the study early if toxicities exceed acceptable parameters. Each individual situation will be reviewed, and response data will be considered. The study will be stopped early if it appears that the benefit no longer outweighs the risks.

12.1 Interventional IIS Janssen Scientific Affairs Requirements for Safety Data Collection and Reporting

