12.1.3 Definitions

Adverse Event (AE)

An adverse event is any untoward medical occurrence in a clinical study subject administered a medicinal (investigational or non-investigational) product. An adverse event does not necessarily have a causal relationship with the treatment. An adverse event can therefore be

any unfavorable and unintended sign (including an abnormal finding), symptom, or disease temporally associated with the use of a medicinal (investigational or non-investigational) product, whether or not related to that medicinal (investigational or non-investigational) product. (Definition per International Conference on Harmonisation [ICH])

This includes any occurrence that is new in onset or aggravated in severity or frequency from the baseline condition, or abnormal results of diagnostic procedures, including laboratory test abnormalities.

Adverse Events of Special Interest

Adverse events of special interest are events that Janssen Scientific Affairs, LLC is actively monitoring as a result of a previously identified signal (even if non-serious). These adverse events are:

- Infusion reactions: \geq grade 3
- Infections: \geq grade 4
- Cytopenias: \geq grade 4
- Tumor lysis syndrome
- Other malignancies
- Intravascular hemolysis – all grades

Any Adverse Event of Special Interest that is to be reported to the COMPANY should be recorded on a Serious Adverse Event Report Form and be reported to the COMPANY within 24 hours of knowledge of the event.

Individual Case Safety Report (ICSR)

A valid ICSR must contain the four minimum criteria required to meet regulatory reporting requirements.

- an identifiable subject (but not disclosing personal information such as the subject's name, initials or address)
- an identifiable reporter (investigational site)
- a Janssen medicinal product
- an adverse event, outcome, or certain special situations

The minimum information required is:

- suspected Janssen medicinal product (doses, indication)
- date of therapy (start and end date, if available)
- batch or lot number, if available
- subject details (subject ID and country)
- gender
- age at AE onset
- reporter ID
- adverse event detail (AE verbatim in English), onset date, relatedness, causality, action taken, outcome, (if available)
- Janssen protocol ID

Product Quality Complaint (PQC)

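### The Section 11.2 stop criterion weighs a drug-related death the same as a Grade 4 laboratory value, so two related deaths in the first five patients do not meet it

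*Combined protocol and SAP*

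**What the plan says.** Section 11.2 closes the study temporarily once the first five patients have completed at least three doses, and the Medical Monitor then reviews the safety results. Three sentences govern what follows.

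- **Stop criterion.** "The recommendation is to consider stopping the study for safety concerns" if, in that period, "3 or more grade 4 or 5 adverse events clearly related to study drug are recorded". The unit is the event, and Grades 4 and 5 share one count.
- **Schedule criterion.** "If 3 or more out of the first 5 patients experience a Grade 3 infusion reaction clearly related to study drug" in the first three doses, the protocol is re-evaluated. The unit here is the patient.
- **Re-opening.** "If fewer than 3 out of the first 5 patients experience a Grade 3 infusion reaction in either of the first 3 doses, the study" re-opens and enrolment expands. Neither Grade 4/5 events nor the Medical Monitor's recommendation appears in this condition.

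Section 12.0 adds that "participant deaths within 30 days of study intervention will be reported to the Medical Monitor within 48 hours". It lets the Medical Monitor and investigators end the study early on judgement of toxicity and of benefit against risk, but says that no criteria for doing so are fixed in advance.

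Section 12.1.3 defines adverse events to include new or worsened conditions "or abnormal results of diagnostic procedures, including laboratory test abnormalities". A Grade 4 laboratory value judged clearly related to the drug is therefore a qualifying event under 11.2.

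**The concern.** Safety and tolerability is the primary objective (Section 1.0), and Section 11.2 holds the plan's only numeric study-level safety criteria. A reader would expect a drug-related death to count for more there than a laboratory grade. It does not: each adds one to a total that must reach three.

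The re-opening sentence compounds this. It is the only place where 11.2 says when enrolment resumes, and a drug-related death has no bearing on it. With two related deaths and fewer than three patients with a Grade 3 infusion reaction, the written criteria contain no prompt to consider stopping and a statement that the study resumes. Whatever holds the study at that point comes from the discretion in 12.0, which itself denies that preset criteria exist.

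**Working it through.** **Plan's own figure.** There is none to reproduce. The documents give no acceptable toxicity rate, error rate or operating characteristic for the criterion, and Section 11.3 says there is no formal hypothesis testing.

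**Direct count (no assumed rate needed).** The input is the threshold in 11.2: at least 3 clearly related Grade 4 or 5 events in 5 patients.

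| Scenario | Qualifying events | Patients affected | Stop criterion |
|---|---|---|---|
| Two related deaths in two patients, nothing else | 2 | 2/5 = 40% | not met |
| Two related deaths plus one related Grade 4 event | 3 | 2/5 or 3/5 | met |
| Three related Grade 4 laboratory events in one patient | 3 | 1/5 = 20% | met |

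The first row assumes that each death is recorded as one Grade 5 event. The third assumes three separately recorded events, each judged clearly related.

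**Re-opening sentence.** In row 1 with no Grade 3 infusion reaction, 0 of 5 is fewer than 3, so the condition is satisfied. It is equally satisfied in rows 2 and 3 if no Grade 3 infusion reaction occurred. The sentence can thus say that the study resumes while the stop criterion is met.

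**Size under assumed rates.** Let p be the probability that a patient has a clearly related death in the window. The documents give no value, so a range is shown. Assume that patients are independent and that deaths are the only qualifying events. With X binomial(5, p), the criterion is unmet when X is 2 or fewer:

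P(X ≤ 2) = (1−p)^5 + 5p(1−p)^4 + 10p²(1−p)³

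At p = 0.20: 0.3277 + 0.4096 + 0.2048 = 0.942. At p = 0.40: 0.0778 + 0.2592 + 0.3456 = 0.683.

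| Assumed p | Criterion unmet, P(X ≤ 2) | Two or more deaths, P(X ≥ 2) | At least one death, P(X ≥ 1) |
|---|---|---|---|
| 5% | 99.9% | 2.3% | 22.6% |
| 10% | 99.1% | 8.1% | 41.0% |
| 20% | 94.2% | 26.3% | 67.2% |
| 30% | 83.7% | 47.2% | 83.2% |
| 40% | 68.3% | 66.3% | 92.2% |

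At p = 20%, two or more deaths occur with probability 26.3% and exactly two with probability 20.5%. So 20.5/26.3 = 78% of the cases with at least two deaths miss the criterion. The last column is the chance that a pause on any related death would be used.

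**Would counting patients instead of events help?** If 3 of 5 patients were required, two deaths would count 2 and still miss. Now let 20% be the assumed per-patient rate of any related Grade 4/5 toxicity, with m qualifying events in each affected patient. An event count of three then needs 3, 2 or 1 affected patients for m = 1, 2 or 3, and is met with probability 5.8%, 26.3% or 67.2%. A patient count of 3 of 5 gives 5.8% whatever m is. Changing the unit would lower sensitivity and leave the two-death case as it is.

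**The case against.** The strongest reply is that this is a prompt for judgement, not a decision rule. The criterion only recommends considering a stop, and it sits inside a closure and Medical Monitor review that take place whatever the count. Section 12.0 brings deaths to the monitor within 48 hours, calls for individual review, and provides for early termination if toxicity becomes unacceptable or benefit no longer outweighs risk. All of this stands. A reader might infer that 12.0 attaches no action to deaths, or that the study would have to continue after two of them. The documents support neither. What is missing is a study-level trigger specific to death.

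It can also be said that the probabilities rest on assumed rates, some of them high. Section 3.1 describes severe reactions in myeloma as rare, under 2% each, and reports no Grade 4 events. That stands too: the table is an illustration, and the direct count carries the argument.

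Finally, a reader might infer from the differing units, or from row 3 of the first table, that event counting is itself the error and that patients should be counted throughout. The two criteria serve different purposes, and counting events is the more cautious choice for a general toxicity prompt. When it is met by clustered laboratory values, the only consequence is that stopping is considered. Section 8.0 does list "Grade 4 hematologic toxicities" as grounds for delaying a patient's dose, but that does not make them irrelevant at study level.

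**Conclusion.** The point holds on the wording of 11.2. Two clearly related deaths among the first five patients do not meet the stop criterion unless a further related Grade 4 event is recorded, and the re-opening sentence disregards them. Sections 11.2 and 12.0 also disagree on whether any criteria are preset.

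The count needs no assumed rate. It rests on one Grade 5 event per death, no other qualifying event, and a literal reading of the re-opening sentence. The 99.9% to 68.3% range depends in addition on the assumed death rates and on independence between patients.

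The consequence is limited by the advisory wording and by the discretionary review in 12.0. This is a gap in the written criteria that should be closed, not evidence that deaths would go unexamined. The event count for Grade 4 toxicity needs no change.

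**What to change.** 1. In 11.2, handle Grade 5 separately: any clearly related Grade 5 event pauses new enrolment until the Medical Monitor has reviewed it and made a written recommendation. Keep the existing event count of three for Grade 4, and do not move to patient counting.
2. Extend the re-opening sentence so that it also requires either that the Grade 4/5 criterion is not met or that the Medical Monitor has recommended continuation.
3. Reconcile the statement in 12.0 that no termination criteria are preset with the criteria in 11.2, for example by cross-reference.

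The edit is a few sentences across two sections. The price is a short enrolment pause after a related death. Deaths within 30 days of study intervention are already due to reach the monitor within 48 hours, so little new process is needed. On the assumptions above, the pause would be used with probability 22.6% at a 5% death rate and 67.2% at 20%.

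The documents do not show whether the interim review has taken place. If it has, record how the criterion and the re-opening sentence were applied.

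### Section 11.2 counts Grade 3 infusion reactions apart from Grade 4-5 events, so a worse set of reactions can leave both interim limits unmet and the study re-opening

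*Combined protocol and SAP*

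**What the plan says.** Under Section 11.2 the study is "temporary closed for an interim analysis after the first 5 patients have completed at least 3 doses". Three sentences then govern the decision.

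- **Stopping limb.** Stopping is to be considered if "3 or more grade 4 or 5 adverse events clearly related to study drug are recorded". This counts events of any type, not patients.
- **Infusion-reaction limb.** The protocol is re-evaluated, with a view to changing the schedule, "If 3 or more out of the first 5 patients experience a Grade 3 infusion reaction clearly related to study drug". This counts patients and names Grade 3 only.
- **Re-opening.** The condition is "If fewer than 3 out of the first 5 patients experience a Grade 3 infusion reaction in either of the first 3 doses", and the consequence is that "the study will re-open and enrollment will be expanded to an additional cohort of subjects". The Grade 4-5 count is not mentioned.

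The same section provides for discretion: "At this time the Medical Monitor will review the safety results of the study".

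Elsewhere Grade 3 and above is sometimes one class. Section 8.0 has "Permanent discontinuation of daratumumab should be undertaken if a third Grade 3 or greater reaction occurs", and Section 12.1.3 lists infusion reactions of Grade 3 and above as one adverse event of special interest. Section 8.0 also gives Grade 3 and Grade 4 reactions separate instructions, so a bare Grade 3 in this protocol can mean Grade 3 alone.

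**The concern.** A safety rule should never become easier to pass when an outcome gets worse. This one can. Three patients with Grade 3 reactions trigger a re-evaluation. If one of the three reactions is Grade 4 instead, the Grade 3 count falls to two, the Grade 4-5 count is one, and neither limb is met. The written outcome is then expansion.

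Infusion reactions are the primary endpoint (Sections 1.0 and 11.3). Section 11.2 holds the only numeric toxicity limits at study level; Section 12.0 says that no criteria for early termination have been set in advance. The decision governs the remaining 25 - 5 = 20 planned patients (Section 11.1).

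The re-opening sentence has a second gap. Three related Grade 4-5 events of any kind, with fewer than three Grade 3 infusion reactions, satisfy both the advice to consider stopping and the statement that the study re-opens.

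**Working it through.** The plan states no operating characteristic for this rule, so there is no figure to reproduce.

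**Inputs.** From 11.2: five patients; limits of three Grade 4-5 events and three patients with a Grade 3 infusion reaction. Section 3.1 gives, for myeloma, 46% infusion reactions of any grade at the first infusion, individual severe reactions as rare (under 2% each) and no Grade 4 events. It gives no pooled Grade 3 or Grade 4 infusion-reaction rate, so both are assumed over a range.

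**Assumptions.** Each patient is classed by worst infusion reaction: Grade 3 with probability p3, Grade 4-5 with probability p4, otherwise q = 1 - p3 - p4. Each Grade 4-5 patient contributes one event, there are no other Grade 4-5 events, all are clearly related, and all five patients count.

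**Step 1: which outcomes slip through.** Write (a, b) for the numbers of patients with Grade 3 and Grade 4-5 reactions. Neither limb is met when a ≤ 2 and b ≤ 2. Requiring a + b ≥ 3 as well leaves (2,1), (1,2) and (2,2). The most severe reactions possible with neither limb met is therefore 2 + 2 = 4 of 5.

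**Step 2: their probability.** P(a,b) = 5!/(a! b! (5-a-b)!) × p3^a × p4^b × q^(5-a-b). The coefficient is 30 for all three splits, so

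gap = 30·p3²·p4·q² + 30·p3·p4²·q² + 30·p3²·p4²·q.

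- p3 = 0.08, p4 = 0.02, q = 0.90: 30×0.0064×0.02×0.81 + 30×0.08×0.0004×0.81 + 30×0.0064×0.0004×0.90 = 0.0031 + 0.0008 + 0.0001 = 0.0040.
- p3 = 0.30, p4 = 0.10, q = 0.60: 30×0.09×0.10×0.36 + 30×0.30×0.01×0.36 + 30×0.09×0.01×0.60 = 0.0972 + 0.0324 + 0.0162 = 0.1458.

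**Step 3: all outcomes with at least three severe reactions.** With s = p3 + p4, P = 10s³(1-s)² + 5s⁴(1-s) + s⁵. At s = 0.4: 0.2304 + 0.0768 + 0.0102 = 0.3174.

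| p3 | p4 | (2,1) | (1,2) | (2,2) | Gap | P(≥3 of 5 severe) | Gap as share |
|---|---|---|---|---|---|---|---|
| 0.08 | 0.02 | 0.0031 | 0.0008 | 0.0001 | 0.004 | 0.009 | 46% |
| 0.10 | 0.02 | 0.0046 | 0.0009 | 0.0001 | 0.006 | 0.014 | 40% |
| 0.20 | 0.02 | 0.0146 | 0.0015 | 0.0004 | 0.016 | 0.074 | 22% |
| 0.30 | 0.02 | 0.0250 | 0.0017 | 0.0007 | 0.027 | 0.190 | 14% |
| 0.30 | 0.10 | 0.0972 | 0.0324 | 0.0162 | 0.146 | 0.317 | 46% |
| 0.30 | 0.20 | 0.1350 | 0.0900 | 0.0540 | 0.279 | 0.500 | 56% |
| 0.40 | 0.10 | 0.1200 | 0.0300 | 0.0240 | 0.174 | 0.500 | 35% |
| 0.40 | 0.20 | 0.1536 | 0.0768 | 0.0768 | 0.307 | 0.683 | 45% |

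**Step 4: effect of a pooled count.** Any outcome that meets a limb under these assumptions has at least three severe reactions. Counting Grade 3 and above together therefore raises the chance of an interim trigger by exactly the gap: from 0.0046 to 0.0086 in the first row, and from 0.1716 to 0.3174 at p3 = 0.30, p4 = 0.10. The most severe reactions compatible with re-opening falls from four to two.

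**The case against.** **The rates.** The only figures in the documents, from myeloma, point to rare severe reactions and no Grade 4 events. The upper four rows of the table are the closer match to them, and there the gap is small. This stands, though patients with AL amyloidosis may differ, and a safety gate is written for the case where they do.

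**The upward lean of the model.** The stopping limb counts every related Grade 4-5 event. Cytopenias or infections, or one reaction recorded as several events, could bring it to three sooner. A patient with Grade 3 at one dose and Grade 4 at another would count in both limbs. This stands too, but where the stopping limb is met that way, the re-opening sentence can still be satisfied and the two instructions then conflict.

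**Discretion.** Both limbs are advisory, the Medical Monitor sees all safety results at the pause, and Section 12.0 allows early termination at any time. A reader might infer that the trial would re-open automatically after four severe reactions in five patients. The documents do not support that: re-opening is what the sentence prescribes, not a certain outcome. Four of five is also an extreme case; the two three-of-five splits carry most of the gap in every row.

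**Consistency.** A reader might also infer that Section 8.0 always treats Grade 3 and above as one class. It does so only in the sentence on a third reaction; Section 12.1.3 does so for expedited reporting. Grade 3 in 11.2 may be shorthand for at least Grade 3, but the text does not say so.

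**Conclusion.** The wording fault holds. As written, the rule is not monotone in severity on the primary endpoint, and its re-opening sentence disregards the Grade 4-5 limb. Its size depends on rates that the documents do not give: about 0.4-3% with Grade 4 reactions at 2% and Grade 3 at 8-30%, and 15-31% with Grade 4 at 10-20% and Grade 3 at 30-40%. The higher range should not be read as a forecast for this trial; nothing in the documents supports those rates as expected values. Both ranges assume one Grade 4-5 event per affected patient and no others. The point is worth correcting because the decision rule is short, concerns the main question of the study, and can be repaired cheaply. It does not show that the three-of-five limit is clinically wrong.

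**What to change.** Reconcile Section 11.2 with the pooled wording in the third-reaction sentence of Section 8.0 and in Section 12.1.3.

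1. In both the re-evaluation and the re-opening sentence, state which grades the by-patient infusion-reaction count covers, so that a Grade 4-5 reaction does not drop out of it. For example, say Grade 3 or higher and keep the sponsor's limit of three of five.
2. Make re-opening conditional on neither limb being met.

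The separate Grade 4-5 limb can stay as it is, and doses and patient management are untouched. The price is a few words and a higher chance of a protocol re-evaluation at the interim, equal to the gap in the table: slight if Grade 4 reactions are rare, larger only if severe reactions are common.
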